## Treatment-related Adverse Events

Any AE with a relationship to study treatment of “Possibly Related” or “Definitely Related” or missing will be considered a treatment-related AE as determined by the Investigator.

## Study Day 1

The first day of medication administered.

## Study Day

Study day is defined as the number of days from Study Day 1.

- Before Study Day 1, Study Day = (Date of Interest – Date of Study Day 1)

- On or After Study Day 1, Study Day = (Date of Interest – Date of Study Day 1) + 1

Therefore, the day prior to Study Day 1 is -1.

### **Analysis Visit Window**

Analysis window won't be required for this study. The unscheduled post-Baseline values will be excluded from the summary table, but only listed.

## **9.0 Analysis Sets**

### **9.1 Intention-to-Treat**

The 'Intent-to-Treat' (ITT) analysis set will include all randomized subjects. The ITT population will be the primary population for all efficacy analyses.

### **9.2 All Treated**

The "All-treated" analysis set will consist of all subjects receiving at least one application of study drug. All safety analyses will be performed on the all-treated analysis set.

### **9.3 Per Protocol**

The Per-Protocol (PP) analysis set will include all subjects in the ITT population who complete 6 weeks of treatment and 12 weeks of post-treatment efficacy evaluation without any major deviations from the protocol. The subjects to be included in the PP analysis population will be determined by the Sponsor prior to the unblinding of the study. The PP population will be used as secondary for the primary endpoint only.

Subjects potentially excluded from the PP population will be based on the following criteria and reviewed by the clinical team:

- 1 - Subjects who have not completed 6 weeks of treatment and 12 weeks of post-treatment efficacy evaluations
- 2- Subjects less than 2 years of age
- 3 - Subjects with more than 6 common warts at baseline
- 4 - Subjects without a pre-treatment wart assessment
- 5 - Subject who have taken an excluded prior and concomitant medications / therapies as listed in the protocol
- 6 - Subjects whose warts are not present for at least 4 weeks before treatment (baseline) as reported in Medical History
- 7 - Subjects with clinically significant dermatological disorders in the treatment area
- 8 - Subjects who require ongoing treatment with furosemide
- 9 - Subjects whose study drug compliance is as follows: missing more than 12 doses in total throughout the study
- 10 - Subjects with week 18 visits out of window more than 14 days outside the target visit date

---

- 11 - Subjects who received the wrong assigned treatment medication
- 12 – Subjects who violated key inclusion/exclusion criteria

Subject listings will be provided to the Sponsor based on the above criteria for review and final determination of the PP population. Subjects to be excluded from the PP will be determined before the study is unblinded and listed in a separate document.

## 10.0 Interim Analyses

No interim analyses are planned for this study.

## 11.0 Data Review

### 11.1 Data Handling and Transfer

Data will be entered and exported as SAS® version 9.4 or higher datasets. Converted datasets will be created using SAS and following standard Clinical Data Interchange Standards Consortium Standard Data Tabulation Model (CDISC SDTM, version 1.3, Implementation Guide version v3.1.3) conventions. Analysis datasets will be created using SAS and following CDISC Analysis Data Model (ADaM, version 2.1, Implementation Guide 1.0) standards.

Medical history and AEs will be coded using the Medical Dictionary for Regulatory Activities (MedDRA), version 21.0 at the time of the analysis to assign a system organ class (SOC) and preferred term (PT) to each event. Prior and concomitant medications and steroids will be coded using the World Health Organization Drug Dictionary 2018MAR01 DDE + HD at the time of the analysis.

Additional details can be found in the █ Data Management Plan for this study.

### 11.2 Data Screening

Beyond the data screening built into the █ Data Management Plan, the █ programming of analysis datasets, tables, figures, and listings (TFL) provides additional data screening. Presumed data issues will be output into SAS logs identified by the word “Problem” and extracted from the logs by a SAS macro and sent to Data Management.

Review of a pre-freeze TFL run on clean subjects and a post- freeze TFL run on the frozen database allow for further data screening prior to lock. The post- freeze TFL will be discussed with the sponsor in a data review meeting to identify any final data issues and seek corrections prior to database lock. The █ statistician and the sponsor must approve database lock.

## 12.0 Statistical Methods

All statistical analyses will be performed using SAS version 9.4 or higher.

The final analysis will be performed at the end of the study (end of trial) after all subjects have completed the Week 18 assessments and the Week 30 follow-up assessments or terminated early. Please note that only the subset of subjects who achieved clearance of at least one treated wart at

---

Week 18/End of Post-treatment Efficacy Evaluation period will continue to the Follow-up period.

Unless otherwise specified, descriptive data summaries will be tabulated for all endpoints. Categorical data will be summarized using number of subjects (n), frequency and percentages of subjects falling into each category, with the denominator for percentages being the number of subjects in the study population, unless otherwise noted. Percentages will be rounded to one decimal place except for 100%, which will have no decimal place. Counts of zero will not display a percentage.

All continuous variables will be summarized using mean, standard deviation, median, minimum, maximum, and number of subjects with observations. The mean and median will be presented to one decimal place greater than the original data, standard deviation will be to two decimal places greater than the original data, and the minimum and maximum will have the same number of decimal places as the original data.

## 12.1 Subject Disposition

The number and percentage of subjects in ITT analysis set will be summarized. A listing by subject will be provided to indicate which subjects are included in each analysis set.

The number and percentage of subjects enrolled, ITT analysis set, All-Treated analysis set, Per-Protocol analysis set, who complete the study and who are in Follow-up period will be presented by treatment, together with the number and percentage of subjects who withdrew from the study prematurely and a breakdown of the corresponding reasons for withdrawal.

A listing of all subjects' analysis set inclusions, disposition, and subjects who discontinued will be presented.

## 12.2 Important Protocol Deviations

Important protocol deviations (IPD) are a subset of protocol deviations that might significantly affect the completeness, accuracy, and/or reliability of the study data or that might significantly affect a subject's rights, safety, or well-being.

Protocol deviations will be determined based on programmed checks of the study database. These Protocol deviations are based on the following categories deemed to be important:

1. Subjects that violate key inclusion/exclusion criteria
2. Subjects who received the wrong treatment
3. Subjects who received prohibited medications/treatment during the trial
4. Subjects who met withdrawal criteria but were not withdrawn
5. Subjects who did not have necessary data collected to interpret the primary endpoint
  - a. Missed Week 18 visit
  - b. Week 18 more than 14 days outside target visit date
6. Subjects with a deviation that significantly affects safety or well-being
  - a. Physical exam, labs or ECG not performed at screening prior to randomization
  - b. Week 6 physical exam or labs not performed
  - c. Pregnancy test not preformed prior to randomization
  - d. Pregnancy test not performed at Week 6

---

For reporting proposed Protocol Deviations will be assigned to the following categories: Inclusion Criteria, Exclusion Criteria, Study Drug, Assessment Safety, Visit Window, and Prohibited concomitant medications.

The protocol deviation list will be finalized prior to the database lock, and important protocol deviation data will be listed and tabulated using incidence by deviation type.

## 12.3 Treatments

### 12.3.1 Extent of Study Drug Exposure

Exposure to study drug (e.g. at least 1 dose etc.), duration of exposure, and number of missed doses (Day 1-Week 2, Week 2-Week 4, Week 4-Week 6) will be summarized by group for the All-Treated analysis set. Summary statistics will be provided for total duration (days) of study drug exposure and treatment compliance for the All-Treated analysis set.

Duration of exposure will be defined as the total number of days a subject was exposed to study drug, calculated as (last dose date - first dose date+1).

Study drug dosing information will be presented by subject in data listings

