### 7.2.1. Inclusion Criteria

1. Subjects, and/or their legal guardians for subjects under the legal age of consent, who provide written informed consent to participate in the study. Subjects who are under the legal age of consent are to provide written informed assent to participate in the study as required, according to IRB guidelines for obtaining assent.
2. Male or female subjects 2 years of age or older.
3. Females of childbearing potential who are using a highly effective form of birth control or females of non-childbearing potential (as specified below).
  - Non-childbearing potential females are defined as females who are premenarchal, or postmenopausal (12 months with no menstrual period without an alternative medical cause), or who have undergone a hysterectomy, bilateral oophorectomy, tubal ligation, or bilateral occlusion of the fallopian tubes (e.g., Essure®) with post-placement confirmation of complete blockage.
  - Highly effective methods of birth control are defined as those, alone or in combination, that result in a low failure rate (i.e. less than 1% per year) when used consistently and correctly.
    - Forms of birth control include: Oral (e.g., birth control pills), Intravaginal (e.g., NuvaRing®), Implantable (e.g., Norplant®), Injectable (e.g., Depo-Provera®) or Transdermal (e.g., Ortho Evra®) contraception; Intrauterine device (IUD); double-barrier (e.g., diaphragm or condom with spermicidal gel or foam); a vasectomized partner or abstinence from heterosexual intercourse when in line with preferred and usual lifestyle of subject (periodic abstinence e.g., calendar, ovulation, sympto-thermal, post-ovulation methods and withdrawal are not acceptable methods of contraception).
      - If an abstinent subject of childbearing potential becomes sexually active during the study, the subject must be willing to use effective birth control as described.
    - For subjects using an acceptable hormonal based form of birth control (e.g., oral birth control, Norplant), she must have been doing so for at least three (3) months prior to the Baseline Visit and be willing to continue stable birth control methods throughout the study.
4. Females of childbearing potential with a negative in-office urine pregnancy test at Screening and Baseline (prior to being randomized to receive study drug).

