5. Subjects must have 1 to 6 clearly identifiable common warts (*verruca vulgaris*). For clarity, subjects must not have > 6 cutaneous common warts at Baseline. All of the common warts must meet the following criteria at Baseline:
  - Warts must be located on hands (dorsal, periungual, or palmar), feet (dorsal), limbs, and/or trunk,
  - Each wart must measure 3 to 10 mm in their longest dimension (diameter) on the epidermal plane of the skin at the baseline visit,
  - Each wart must be present for at least 4 weeks at the baseline visit,
  - Plantar, facial, subungual, and other warts (e.g., flat, genital) are excluded from treatment (i.e., these wart types are excluded from treatment, however the subject is not excluded).
6. Subjects free of any clinically significant dermatologic disorder in the treatment area (e.g., eczema, psoriasis, atopic dermatitis, etc.).
7. Subjects free of any clinically significant systemic condition which, in the opinion of the investigator, will interfere with the study assessments or increase the risk of AEs.
8. Subjects willing to refrain from using other topical products in the treatment area, or prohibited medications for the duration of the study (refer to Section 7.6.10.1).
9. Subjects able and willing to comply with all study procedures, restrictions and visit requirements.

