### 7.6.2. Treatment Administration

Subjects will be instructed to apply a small amount of gel [approximately 20-30 mg CLS006 (equivalent to 0.025-0.0375 mg of furosemide)] to cover each wart identified at baseline once daily for 6 weeks (42 consecutive days). Subjects will be instructed to gently rub the gel into each wart for approximately 20 seconds or until the gel is fully absorbed.

Subjects (or caregivers) will apply study drug to each “Baseline Treatment” wart one time per day for the entire treatment period or until instructed to stop by study personnel.

- \* If clinical clearance of a wart is determined **by the PI or an appropriately qualified Sub-I**, subjects should be instructed to stop applying study drug to that specific “wart” (spot) only.
- Merging/Confluent warts should be treated with a small amount of study drug to cover the merged/confluent wart.
- Cluster/Satellite (Splitting) warts should be treated with a small amount of study drug to cover the area (to the outermost wart) considered part of the wart cluster/satellite.

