### 7.7.2. Sample Size Determination

The sample size estimates for the current study are based upon the rates of clearance of warts in the previous Phase 2 study [REDACTED]. This was a randomized, double-blind, vehicle-controlled, Phase II study in 80 subjects who were treated with topical [REDACTED], furosemide, [REDACTED], or vehicle for 42 days daily with an 8-week follow-up period. For the furosemide treatment group, the proportion of subjects with all cleared warts was 0.1 (10%) versus 0 in the vehicle.

The difference in the proportion of subjects with all treated warts cleared (complete clearance) at the Week 18/End of Post-treatment Efficacy Evaluation period (is the primary endpoint of the current study. For conservative purposes, assuming 10% and 2% complete clearance rates in the furosemide and vehicle treated groups respectively 200 subjects randomized per treatment group will provide for 92% power at a two-sided  $\alpha$  of 0.05 to detect a difference between active and placebo.

With the inclusion of an additional 80 subjects in the  $\geq 2$  to  $< 12$  cohort, the total sample size of 480 will provide 96% power with the assumption unchanged.

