## 6.2 Randomization

Subjects that meet all inclusion and exclusion criteria will be randomized to one of two treatment groups in a 1:1 ratio for each study center according to a predetermined computer-generated randomization code.

Subjects will be randomized to treatment using an Interactive Web Response System (IWRS). The randomization scheme will include age stratum at 3 levels ( $\geq 2$  to  $< 12$ ,  $\geq 12$  to  $< 18$  or  $\geq 18$ ) and investigative site.

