### **12.6.3 Laboratory Data**

Laboratory test results are reported in International System of Units (SI).

Descriptive summaries of changes from baseline for each laboratory test listed below will be provided for numerical laboratory assessments by visit.

Laboratory shift tables from baseline to each post baseline visit for lab values evaluation of 'High' 'Low' or 'Normal', when available, will be planned when the baseline results are available. The categorical lab results will be summarized by frequency and percentage and by visit.

The clinical safety laboratory tests will include the following parameters:

- Hematology: hemoglobin, hematocrit, red blood cell (RBC) including mean corpuscular volume (MCV) and red cell distribution width (RDW), white blood cell (WBC) count with differential (neutrophils, lymphocytes, monocytes, eosinophils, basophils), and platelet count.
- Chemistry/Lipids:
  - General: calcium, glucose, lactate dehydrogenase (LDH)
  - Electrolytes: carbon dioxide (bicarbonate), chloride, magnesium, sodium, potassium
  - Kidney/Liver: blood urea nitrogen (BUN), creatinine, uric acid, total protein, aspartate aminotransferase (AST), alanine aminotransferase (ALT), albumin, alkaline phosphatase (ALP), gamma glutamyl transferase (GGT), total bilirubin
  - Lipids: total cholesterol, high-density lipoproteins (HDL), low-density lipoproteins (LDL), triglycerides

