### **12.6.4 Vital Signs**

Vital signs (blood pressure [BP], heart rate [HR]) will be measured at each visit during Screening, Double-blind Treatment and Post-treatment Efficacy Evaluation Periods.

Observed values and changes from baseline in vital signs will be summarized by vital sign parameter and visit. Descriptive statistics will be shown for baseline, each post-baseline time point, and the change from baseline to each post-baseline time point.

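### Exposure and safety are tabulated over all ages combined, so the plan gives no adverse-event rates or mean changes by arm within the three randomised age strata, including the 2 to under 12 group

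*SAP*

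**What the plan says.** **Exposure and safety tables.** SAP 12.3.1 reports exposure, its duration and missed doses, which "will be summarized by group for the All-Treated analysis set". The units are days, missed doses and compliance; no amount in mg or mg/kg is derived. SAP 12.6.1 and 12.6.2 tabulate treatment-emergent, serious and special-interest adverse events by system organ class and preferred term. SAP 12.6.3 says "Descriptive summaries of changes from baseline for each laboratory test listed below will be provided for numerical laboratory assessments by visit", and SAP 12.6.4 says "Observed values and changes from baseline in vital signs will be summarized by vital sign parameter and visit". None of these sections mentions age, and neither does Protocol 7.7.9.

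**Age elsewhere in the plan.** Under SAP 6.2, "The randomization scheme will include age stratum at 3 levels". Age group is also used in the baseline table (SAP 12.4), in the imputation model, and as a stratum or covariate for efficacy. SAP 12.5.1 allows an optional look at efficacy by age if the Breslow-Day test fails.

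**Population and amount applied.** Eligibility covers "Male or female subjects 2 years of age or older" (Protocol 7.2.1), and the objective in Protocol 6 covers safety over that range. Protocol 7.7.2 presents the youngest group as a deliberate addition ("With the inclusion of an additional 80 subjects in the" 2 to under 12 cohort). Protocol 7.6.2 sets the amount per wart at "approximately 20-30 mg CLS006 (equivalent to 0.025-0.0375 mg of furosemide"), once daily, with no reference to age or weight. By Protocol 7.2.1, "Subjects must have 1 to 6 clearly identifiable common warts".

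**The concern.** The trial enrols about 80 subjects aged 2 to under 12 and about 80 aged 12 to under 18, and it randomises within these groups. Valid comparisons of arms within age are therefore available, but the plan never tabulates them for safety. About 320 of 480 subjects are adults, so they dominate any pooled rate or mean. Blood pressure and heart rate from toddlers to adults are averaged together, and so are the laboratory changes.

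Age matters here because the gel amount does not scale with body size and Protocol 7.3.1 schedules no pharmacokinetic sampling. SAP 12.6.1 itself looks for systemic effects: its special-interest terms come from classes that include cardiac, renal, metabolic and blood disorders. At stake is whether the report can describe safety in young children with rates and mean changes by arm, or only through individual listings.

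**Working it through.** **1. The plan's own figures.**
- Furosemide per wart: 20 mg x 0.125% = 0.025 mg and 30 mg x 0.125% = 0.0375 mg, as Protocol 7.6.2 states.
- Power for 10% against 2% clearance at two-sided 0.05. With n per arm and p the mean of the two rates, power = Phi{[|p1 - p2| sqrt(n) - 1.96 sqrt(2p(1-p))] / sqrt(p1(1-p1) + p2(1-p2))}. This gives 92.4% at 200 per arm and 96.0% at 240 per arm, matching the stated 92% and 96%.

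**2. Dilution in a pooled table.** Inputs are 480 in total and 80 aged 2 to under 12. At 1:1 that is about 40 of 240 per arm.
- An effect confined to the stratum appears pooled as the effect x 40/240, one sixth of its size. This holds for risk differences and mean shifts.

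**3. Illustration with background events** (assumed rates: 5% on vehicle at all ages; on active, 20% in this stratum and 5% elsewhere).
- Within the stratum: 20% - 5% = 15 points.
- Pooled active rate: (40 x 20% + 200 x 5%)/240 = 18/240 = 7.5%. Pooled difference: 2.5 points.
- Power by the same formula: 53% within the stratum (40 per arm) and 20% pooled (240 per arm).

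**4. A case where pooling costs almost nothing.** Suppose 4 events occur in the 40 treated children and none in anyone else.
- The rate falls from 4/40 = 10% to 4/240 = 1.7%.
- Two-sided Fisher p is 0.116 for 4/40 v 0/40 and 0.123 for 4/240 v 0/240.
- The pooled table therefore hides an effect only when other ages contribute background events, or when the outcome is a mean.

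**5. Nominal amount applied per kg** (a separate matter from step 2). The documents give no typical weights, so these are assumptions. At equal wart counts the ratio is adult weight divided by child weight.

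| Child weight | Ratio to a 60-80 kg adult |
|---|---|
| 10 kg | 6.0-8.0 |
| 15 kg | 4.0-5.3 |
| 20 kg | 3.0-4.0 |
| 30 kg | 2.0-2.7 |
| 40 kg | 1.5-2.0 |

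- The ceiling at any age is 6 warts x 0.0375 mg = 0.225 mg per day. That is 18.8 micrograms/kg at 12 kg, and 2.8 to 3.8 at 80 to 60 kg.
- In the earlier 7-day study (Protocol 5.2), each dose contained 1250 micrograms of each of two components whose names are redacted. If one is furosemide, an assumed 80 to 60 kg subject had 15.6 to 20.8 micrograms/kg, close to the 12 kg ceiling here.

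**6. Precision after a split.** With zero events in 40, the one-sided 95% upper limit is 1 - 0.05^(1/40) = 7.2%.

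**The case against.** The SAP agrees with Protocol 7.7.9; nothing was promised and then dropped. By-subject listings are planned for dosing, baseline data, adverse events, special-interest events, deaths and serious events. Protocol 7.5.6.1 requires any clinically significant change in vital signs or laboratory values to be recorded as an adverse event, so an individual case is not averaged away. Laboratory shift tables count categories as well as means. Descriptive tables by age carry no alpha and could be produced later. Protocol 7.7.1 says the SAP will include mock displays; none are in the text supplied, so table layouts cannot be checked.

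All of this is correct, and it limits the point. A reader might infer that the trial cannot answer its safety question in children, or that age-split tables would be its only evidence on them. The listings, the shift tables and the adverse-event rule contradict that. What they do not give is a rate or mean change by arm within age. Leaving the tables until after unblinding also leaves the age cut-offs open to choice.

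A reader might also join the two ratios and infer that young children receive several times the adult exposure and that this signal is diluted six-fold. The documents do not support that. The largest per-kg ratios apply only near age 2, on assumed weights and equal wart counts; the factor of six belongs to the whole 2 to under 12 stratum. The per-kg figure is also an amount applied, not systemic exposure. It is a ceiling, because application stops on cleared warts. Protocol 5.2 reports that the earlier study's dose was well tolerated, with all levels but one below 50 pg/mL. This lowers the expected risk, although the study had 12 subjects, lasted 7 days, and their ages are not given.

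**Conclusion.** The reporting gap is real: no exposure or safety table in the SAP text is split by age, in a trial that is stratified by age and claims safety from age 2. An effect confined to the 2 to under 12 stratum appears at about one sixth of its size when pooled, provided that the planned 80 of 480 are enrolled. With background events in other ages this can hide a difference (15 points becoming 2.5, on assumed rates); with no background events it barely changes the test.

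Separately, on assumed weights, the nominal amount applied per kg is about 4 to 8 times the adult value at 10 to 15 kg and about 1.5 to 4 times at 20 to 40 kg. That is a reason to look by age, not evidence of harm. The point does not affect the primary analysis; it is a worthwhile, inexpensive improvement to safety reporting.

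**What to change.** Before unblinding, add to SAP 12.6.1 to 12.6.4 a repeat by treatment within the three randomisation age strata, labelled descriptive, of:
- the overall summary of treatment-emergent adverse events, the table by system organ class and preferred term, and the treatment-related events;
- adverse events of special interest;
- laboratory changes and shifts;
- vital-sign changes.

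Repeat the exposure table in SAP 12.3.1 by age stratum as well. Because that table counts days and missed doses, splitting it will not show amounts per kg. Optionally add a nominal furosemide amount per kg per day, calculated as treated warts x 20-30 mg x 0.125% / Screening weight and labelled as the planned maximum applied amount. Wart counts and weight are already collected; no weighing of returned tubes is described, so actual use cannot be derived.

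The cost is SAP wording and repeated table runs. The downside is imprecision: with about 40 per arm in each paediatric stratum, an absence of events should not be read as evidence that rare events do not occur. No change to any dose is proposed.
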